## 13.2 Analysis of Secondary Endpoints

### 13.2.1 Health related quality of life

The primary HRQoL aim is to assess the change from baseline to the end of cycle 6 in the vitality or hormonal function score as well as the sexuality score on the EPIC-26 questionnaire. It is anticipated approximately 75% of patients will have both scores for each domain. A one-sample t-test will be used to assess the overall change in score. To be considered a clinically meaningful difference will be defined as half historical standard deviation for the specific domain. Given 48 evaluable patients, there is 80% power to detect a 0.41 change in the hormonal domain score of the EPIC-26 assuming 2-sided 5% alpha. Results in this study will be evaluated in the context of past research by Sanda et al showing patients that received radiotherapy with non-hormonal therapy had a score on the vitality or hormonal function domain of approximately 80 and a score on the sexuality domain of 26.

Descriptive statistics at each time point and changes over time will be provided for each of the EPIC-26 domains as well as for the PROMIS-Fatigue and PSQ1. Mixed models will be used to explore the impact of time on quality of life adjusting for prognostic baseline factors.

13.2.2 Safety and Tolerability: We will monitor toxicities experienced by all treated patients. Frequency and severity of worst grade 3 or higher treatment-related AEs by type will be reported along with the incidence of overall grade 3 or higher treatment-related AEs. With 71 treated patients, the maximum width of a 90% CI for a given toxicity is 21%. The probability of observing one rare severe toxicity (true rate=5%) is 97%. Tolerability endpoints include the number of dose reductions and treatment interruptions as well as the number of patients that discontinue treatment due to AEs. The safety summary will include clinical laboratory, ECG and vital signs data.

13.2.3 Hormone Levels: Descriptive statistics at each time point and changes over time will be provided for all hormone measures. Paired t-tests and two-sample t-tests (or non-parametric equivalents) will be used to assess significance of change over 6 cycles of treatment in hormone levels for the overall cohort and by status on primary clinical endpoint (yes or no achieving PSA level  $\leq 0.20$  ng/ml at the end of 6 cycles of treatment with enzalutamide and EBRT).

13.2.4. Anthropomorphic Measurements: Descriptive statistics at each time point and change over 6 cycles will be provided for all anthropomorphic measures.

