#### The Expanded-Prostate Index Composite – 26 (EPIC 26)

EPIC-26 evaluates patient's urinary incontinence (4 items), urinary irritation/obstruction (4 items), bowel (6 items), and vitality/hormonal function (5 items). All domains are reported on a scale of 0 – 100. EPIC is a robust prostate cancer HRQoL instrument that measures a broad spectrum of symptoms and has 50 items; however, to decrease patient burden only the domains most pertinent to this study will be used as represented in the EPIC-26. EPIC-26 has been validated in men with localized prostate cancer who underwent surgery, external beam radiation, or brachytherapy with or without the use of hormonal adjuvants. Further information on EPIC can be found at the University of Michigan website: <http://www.med.umich.edu/urology/research/epic.html>.

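### The 0.41 in the EPIC-26 power statement is in SDs of the change score, not score points, and no SD is given to compare it with the half-SD threshold

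*Combined protocol and SAP*

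**What the plan says.** The main quality-of-life aim in section 13.2.1 compares the end of cycle 6 with baseline and looks at change "in the vitality or hormonal function score as well as the sexuality score on the EPIC-26 questionnaire". The test is given as "A one-sample t-test will be used to assess the overall change in score". On completeness the plan says "It is anticipated approximately 75% of patients will have both scores for each domain", and on power, for 48 evaluable patients, "there is 80% power to detect a 0.41 change in the hormonal domain score of the EPIC-26 assuming 2-sided 5% alpha".

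The threshold for importance is worded "To be considered a clinically meaningful difference will be defined as half historical standard deviation for the specific domain". The only historical figures offered are means: men given radiotherapy without hormonal therapy "had a score on the vitality or hormonal function domain of approximately 80 and a score on the sexuality domain of 26". No SD appears for either domain, for the change, or as a correlation between visits.

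Section 9.2.2 describes the instrument and states "All domains are reported on a scale of 0 – 100". It also schedules the questionnaires at baseline, cycle 3 day 1, cycle 5 day 1, end of cycle 6 and 3 months after. Apart from the baseline and end-of-cycle-6 pair, these scores enter descriptive summaries and an exploratory model: "Mixed models will be used to explore the impact of time on quality of life adjusting for prognostic baseline factors".

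**The concern.** The power sentence calls 0.41 a change in a score that runs from 0 to 100, so on its face it claims sensitivity to less than half a point. A reader who wants to know whether the study can see a change of the size the plan calls meaningful has to compare 0.41 with half a historical SD. The two are not in the same unit, and the plan supplies nothing to convert them. The sentence also covers only the hormonal domain, although the aim names two.

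A second matter is how the data are used. A t-test on change needs both scores, so about a quarter of the men are expected to fall out of the main analysis, including any who have cycle 3 or cycle 5 scores. Section 13.1 says how missing PSA values are handled; section 13.2.1 says nothing comparable for quality of life.

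At stake is how the result is read. Section 1.1 expects a better profile than LHRH agonists on these outcomes and looks ahead to a phase III trial, so readers should be able to set the observed change beside a stated threshold in points.

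**Working it through.** **Inputs from the plan.** 71 enrolled, 10% ineligible, 64 evaluable (section 13.1). 75% with both scores, 48 evaluable, two-sided 5%, 80% power, effect 0.41, one-sample t-test (section 13.2.1). Scale 0 to 100 (section 9.2.2).

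**1. Sample size.** 0.75 × 64 = 48, as stated.

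**2. Reproducing 0.41.** For a one-sample t-test, power depends on d = mean change / SD of change, through a noncentral t with 47 degrees of freedom and noncentrality d√48.
- Normal approximation: d = (1.960 + 0.842)/√48 = 2.802/6.928 = 0.404.
- Noncentral t: d = 0.413 for 80% power.
- At d = 0.41 the noncentrality is 0.41 × 6.928 = 2.84 and power is 79.4%.

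The stated figure is therefore the correct standardised effect, rounded. It would also be right in points only if the SD of change were about 1 point on the 0 to 100 scale.

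**3. The same effect in points.** Detectable change = 0.413 × SD of change. The SD is not in the documents, so a range is assumed.

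| Assumed SD of change (points) | Detectable change (points) |
|---|---|
| 10 | 4.1 |
| 15 | 6.2 |
| 20 | 8.3 |
| 25 | 10.3 |

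**4. Comparison with the half-SD threshold.** The threshold is most naturally read as half the SD of the domain score. If the SDs at baseline and at end of cycle 6 both equal the historical SD and the two scores correlate at r, then SD of change = domain SD × √(2(1 − r)). In domain SDs the detectable change is 0.413 × √(2(1 − r)). In SDs of change the threshold is 0.5/√(2(1 − r)).

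| Assumed r | √(2(1 − r)) | Detectable change (domain SD) | Threshold (SD of change) | Power for threshold |
|---|---|---|---|---|
| 0.3 | 1.183 | 0.49 | 0.423 | 82% |
| 0.5 | 1.000 | 0.41 | 0.500 | 92% |
| 0.7 | 0.775 | 0.32 | 0.645 | 99% |

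Power for the threshold drops below 80% only when the SD of change exceeds 0.5/0.413 = 1.21 domain SD, that is, when r is below about 0.27. If the threshold was meant as half an SD of change, power is 92% whatever r is.

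**5. Scores outside the main test.** With 64 men and 48 pairs, 64 − 48 = 16 men are expected not to enter the t-test. The documents do not say which of the two scores they lack or why. Section 6.3 takes men off study after 14 days of missed drug, while the schema notes that men who cannot complete enzalutamide still receive radiotherapy. Missingness could therefore be related to how men fare, or not.

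**The case against.** The strongest reply is that this is a labelling slip. The sentence attaches no unit to 0.41, the sentence before it already speaks in SDs, and the number reproduces as a standardised effect. Enrolment of 71 rests on the PSA endpoint and would not change. Under plausible correlations the study is well powered for its own threshold. All of that stands, and it is why the point is minor. It does not remove the need for correction: the sentence as printed calls 0.41 a change in the domain score, and the SD needed to interpret it is absent.

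On the scores left out of the main test, the defence is that descriptive statistics at every visit and mixed models over time are already planned, the endpoint is secondary, and the study is described as exploratory. That also stands, so the choice of main analysis is an improvement and not an error.

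A reader might infer that the quality-of-life aim is hopelessly underpowered. Taken as 0.41 points, power with 48 men would be only 5.9% to 5.1% for assumed SDs of change of 10 to 25, and 80% power would need roughly 4,700 to 29,000 men. The documents do not support that inference: step 2 shows that the calculation behind the sentence was in SDs of change.

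**Conclusion.** The power statement is wrong as written in its unit and sound in its arithmetic. With 48 men the detectable effect is 0.41 SD of the change score, and the same figure applies to the sexuality domain. No power shortfall is shown. The gap is that the plan cannot be used to compare this effect with its half-SD threshold. Over assumed correlations of 0.3 to 0.7 the detectable change is 0.49 to 0.32 domain SD against 0.50, so the design is probably adequate. That rests on the assumed correlations and on equal SDs at both visits, neither of which the documents give.

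A reader might also infer that the t-test on men with both scores gives a biased answer. The documents do not establish this. There is no bias if scores are missing completely at random; otherwise it could run in either direction, and any size put on it would come from an assumed dropout model. Nor do the documents make a formal rule for showing or excluding a meaningful change a requirement. For a secondary endpoint in an exploratory single-arm study such a rule is optional, as is a sensitivity analysis that shifts the missing scores.

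**What to change.** **Correct the statement.** Say that 48 evaluable men give 80% power, at two-sided 5%, to detect a mean change of 0.41 SD of the change score, for both the hormonal and the sexuality domain. For each domain add the historical SD that defines the threshold, the assumed SD of change, and both quantities in points. This changes wording only.

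**Cheap improvement.** Take the main estimate, the baseline to end-of-cycle-6 contrast, from a longitudinal mixed model on all available scores, with visit as a category. Report it with a 95% confidence interval beside the half-SD threshold, keep the t-test as a supporting analysis, and report the number of scores missing at each visit.

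The questionnaires and visits are already in the plan, so no new data are needed. It does re-specify the exploratory mixed model, and the text should state how the baseline score enters, whether the prognostic covariates stay, and whether the 3-month score is included. The downside is that the model relies on scores being missing at random; if missingness depends on the unseen final score, bias can remain.

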### 1.3 Secondary Objectives

1. Assessment of the effect of treatment on health-related quality of life including fatigue, sleep quality, as well as urinary, bowel, sexual and hormonal functioning.
2. Assessment of the effect of treatment on serum sex hormones including androgens and estrogens.
3. Assessment of the effect of treatment on body fat distribution and muscle mass.
4. Assessment of safety and tolerability according to adverse event reporting during the trial.
5. Assessment of the effect of treatment on bone metabolism.

CONFIDENTIAL

This document is confidential. Do not disclose or use except as authorized.

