Fatigue was the most frequently reported adverse event, with dose-dependent increases of Grade 3 fatigue (0% at 150 mg/day, 9% at 240 mg/day, 15% at 360 mg/day, and 20% at 480 mg/day). The dose of 240 mg/day was defined as the maximum tolerated dose. At doses of 240 mg and above, an increasing proportion of patients needed dose reductions for fatigue. Dose reductions were needed in 1 of 29 patients (3%) that received 240 mg/day, 3 of 28 patients (11%) that received 360 mg/day, and 5 of 22 patients (23%) that received 480 mg/day, and 0 of 58 patients that received 30, 60, or 150 mg/day. After dose reductions, the symptoms resolved. Only 1 patient discontinued treatment due to fatigue with an onset coinciding with prostate specific antigen (PSA) rise. Overall, the most common mild (grade 2) adverse events were fatigue ( $n = 38$  [27.1%]), nausea ( $n = 12$  [8.6%]), dyspnea ( $n = 11$  [7.9%]), anorexia ( $n = 8$  [5.7%]), and back pain ( $n = 8$  [5.7%]). Fatigue, nausea, and anorexia were the only mild adverse events with an increasing incidence as the dose of enzalutamide was increased. None of the grade 2 events required dose modification or the discontinuation of treatment, apart from 1 patient treated at 480 mg/day who had nausea at baseline and stopped therapy after 7 weeks.

CONFIDENTIAL

This document is confidential. Do not disclose or use except as authorized.

Version 13.0 Protocol Version Date: 1/09/2015

In the randomized clinical trial, 7 of 800 (0.9%) patients treated with enzalutamide 160 mg once daily experienced a seizure. No seizures occurred in patients treated with placebo. Seizures occurred from 31 to 603 days after initiation of enzalutamide. Patients experiencing seizure were permanently discontinued from therapy and all seizures resolved. There is no clinical trial experience re-administering enzalutamide to patients who experienced seizures.

The safety of enzalutamide in patients with predisposing factors for seizure is not known because these patients were excluded from the trial. These exclusion criteria included a history of seizure, underlying brain injury with loss of consciousness, transient ischemic attack within the past 12 months, cerebral vascular accident, brain metastases, brain arteriovenous malformation or the use of concomitant medications that may lower the seizure threshold.

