### **2.3 Rationale**

Presently most patients with intermediate risk prostate cancer receive neoadjuvant, concurrent and adjuvant hormonal therapy with external beam irradiation. Multiple studies have shown that the addition of HT improves survival to external beam radiation (5,6) However androgen deprivation induced by LH-RH agonists consistently results in hot flashes, loss of libido, loss of sexual functioning, weight gain, changes in metabolism, loss of muscle mass and fatigue (7, 8).

In contrast, treatment with the anti-androgens bicalutamide or flutamide has minimal side effects, likely related to the fact that these agents do not suppress serum testosterone. Enzalutamide has the potential to have similar anti-tumor effects as LH-RH agonist without the toxicity associated with castrate testosterone levels. If it were shown that enzalutamide (enzalutamide) could be used as an effective adjuvant treatment for prostate cancer without androgen deprivation it would have dramatic and significant impact, including expanding its use to those patients who may have more intermediate risk and/or are unable to tolerate the toxicities associated with androgen deprivation

We have chosen as the primary endpoint the assessment of the proportion of patients whose PSA level is  $\leq 0.2$  ng/ml at the conclusion of therapy. This endpoint was chosen because patients that

CONFIDENTIAL

This document is confidential. Do not disclose or use except as authorized.

Version 13.0 Protocol Version Date: 1/09/2015

achieve this value after treatment with LHRH analogs in combination with EBRT have an excellent prognosis compared to patients that demonstrate higher PSA levels (1, 9). Furthermore, demonstration of PSA levels of  $\leq 0.2\text{ng/ml}$  in a significant number of patients treated on this study would be strong motivation to perform a phase III randomized trial comparing enzalutamide to LHRH analog therapy in the same setting.

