#### **6.1.3 Enzalutamide**

##### Common

- Peripheral Edema
- Flushing
- Diarrhea
- Neutropenia
- Arthralgia
- Musculoskeletal pain
- Fatigue
- Gynecomastia

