#### 6.2.1.3 Management of gynecomastia

At the discretion of the treating physician, at any time before or during treatment patients are permitted to receive radiation therapy to the breasts to prevent or treat gynecomastia. Treatments such as tamoxifen are not permitted for gynecomastia.

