#### 6.2.2 Management of enzalutamide toxicity

6.2.2.1 If Grade 1–2 toxicities occur, give supportive care per institutional guidelines. No enzalutamide dose reduction should occur. However, at the discretion of the treating physician, an investigator can hold enzalutamide for intolerable Grade 2 toxicity for a maximum of 14 days. Participants should resume enzalutamide at the original dose (160 mg/day). If the participant is not able to resume study medication after being held for 14 days, the participant must be permanently removed from the study.

6.2.2.2 If Grade 3 fatigue occurs, hold enzalutamide and contact the medical monitor for appropriate instructions on dose reduction.

6.2.2.3 If Grade 3 or higher toxicities occur that are considered potentially related to enzalutamide including headache (that interferes with activities of daily living [ADL]), nausea (requiring total parenteral nutrition or intravenous fluids), vomiting (> 6 episodes/24 hours requiring total parenteral nutrition or intravenous fluids), diarrhea (requiring intravenous fluids or hospitalization, or resulting in hemodynamic collapse), or any other toxicity where patient safety is jeopardized, hold enzalutamide. When the toxicity has resolved to ≤ Grade 1, resume study medication at the full dose. Prophylactic medications should be considered as appropriate. If toxicity recurs, hold study medication and adjust or add medications to mitigate the toxicity. When the recurrent toxicity has resolved to ≤ Grade 1, resume enzalutamide at 120 mg/day (3 pills /day). This should be done with the approval of the PI and the medical monitor.

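### The adverse event tables in Section 13.2.2 stop at grade 3 and the yes/no breast question has no planned analysis, so the plan yields no incidence of breast events below grade 3

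*Combined protocol and SAP*

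**What the plan says.** Safety is a secondary objective in Section 1.3: "Assessment of safety and tolerability according to adverse event reporting during the trial". The analysis commitment is in Section 13.2.2: "Frequency and severity of worst grade 3 or higher treatment-related AEs by type will be reported". The overall incidence promised in the same sentence has the same grade and attribution limits. Section 13.2.2 also counts dose reductions, treatment interruptions and discontinuations due to adverse events, with no grade limit but not by type.

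Breast effects appear in several places:

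- Section 6.1.3 lists "Gynecomastia" under common effects of enzalutamide, without a grade.
- Section 6.2.1.3 says that "patients are permitted to receive radiation therapy to the breasts to prevent or treat gynecomastia".
- The Section 8 calendar schedules a caliper measurement at baseline, Cycle 4 Day 1 and end of cycle 6. Its last footnote adds a yes/no question on tenderness and/or enlargement at every study visit.
- EPIC-26 (Appendix C) item 13b asks about breast tenderness or enlargement.

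Section 10.2 requires all adverse events to be recorded on case report forms. Section 9.2.1 restricts reporting by attribution and mentions no grade. Section 13 names neither the yes/no question nor breast irradiation.

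**The concern.** The case for the drug in Section 2.3 is one of tolerability as well as activity: "Enzalutamide has the potential to have similar anti-tumor effects as LH-RH agonist without the toxicity associated with castrate testosterone levels". Breast change is a cost that the protocol expects, measures and permits to be treated. Readers weighing the drug against an LH-RH agonist will want to know how many men had it. A by-type table that starts at grade 3 answers that only for severe cases.

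The protocol's own background shows how a grade 3 cut-off can hide a frequent effect. Section 2.1.1 reports that "Fatigue was the most frequently reported adverse event, with dose-dependent increases of Grade 3 fatigue (0% at 150 mg/day", and that none of the 58 men on 30 to 150 mg/day needed a dose reduction. Yet "the most common mild (grade 2) adverse events were fatigue", at 38 of 140 (27.1%) over all doses. At stake is a trial report that follows the plan exactly and shows a cleaner tolerability profile than the data collected would support.

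**Working it through.** **1. The plan's own precision figures.** Section 13.2.2 gives 71 treated patients, a maximum 90% CI width of 21%, and a 97% probability of observing one toxicity with a true rate of 5%.

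- Exact (Clopper-Pearson) 90% limits for x events in n = 71 are the 5% quantile of Beta(x, n − x + 1) and the 95% quantile of Beta(x + 1, n − x). Over all x the widest interval is 20.6 points, at x = 35 or 36. This agrees with 21%.
- P(at least one event) = 1 − 0.95^71 = 0.974. This agrees with 97%, reading one as at least one.

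**2. Which planned analyses could yield a breast-event incidence?**

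| Source | Planned analysis | Incidence below grade 3? |
|---|---|---|
| AE forms (10.2) | By type and overall, grade 3 or higher, treatment-related (13.2.2) | No |
| Dose reductions, interruptions | Counts (13.2.2) | No: not by type |
| Discontinuations due to AEs | Count at any grade (13.2.2) | No: not by type, and only men who stop |
| EPIC-26 item 13b | Part of the hormonal domain score (13.2.1) | No: combined with four other items |
| Caliper diameter and size grade | Plausibly 13.2.4 | No case definition; tenderness not captured |
| Yes/no question | None | No |
| Breast irradiation (6.2.1.3) | None | No |

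On reductions and interruptions, Section 6.2.2.1 says of grade 1–2 toxicity: "No enzalutamide dose reduction should occur". It allows a hold only for intolerable grade 2. Breast events that are grade 1 or tolerated grade 2 should therefore produce neither.

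On the calipers, the assessment is written under Section 9.4, and Section 13.2.4 promises descriptive statistics for all anthropomorphic measures. But the Section 9.4 list and calendar footnote 3 name only triceps, biceps, shoulder blade and waist, and breast assessment has its own calendar row. The size grade starts at 2 cm or less as grade 1, with no category for none, so read literally a change from 0 to 2.0 cm does not move the grade. The recorded diameter would show it.

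**3. What the cut-off could hide.** The documents give no breast-event rate. The counts below are assumptions, as is the premise that every event is below grade 3. The middle count scales the fatigue figure: 71 × 38/140 = 19.3.

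| Assumed men affected | Planned table, grade 3 or higher | Any-grade count (exact 90% CI) |
|---|---|---|
| 7/71 = 9.9% | 0/71 (0% to 4.1%) | 4.7% to 17.7% |
| 19/71 = 26.8% | 0/71 (0% to 4.1%) | 18.3% to 36.7% |
| 35/71 = 49.3% | 0/71 (0% to 4.1%) | 39.0% to 59.6% |

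The upper limit for zero events is 1 − 0.05^(1/71) = 0.041. The planned column is the same whatever the true number of lower-grade events. Every any-grade interval lies within the 21-point maximum already stated.

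**The case against.** The strongest reply is that breast effects are already covered. Item 13b is one of five items in the EPIC-26 hormonal domain, whose change is formally tested, so breast symptoms of any severity feed the main quality-of-life result. The Section 9.4 list is worded as inclusive, so diameter probably falls under Section 13.2.4, where growth would show even if the size grade did not move. Discontinuations are counted whatever the grade. Section 13.2.2 does not say that only grade 3 events may be reported, and Section 9.2.1 sets no grade limit, so the table can be read as a minimum.

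Much of this stands, and it rules out a stronger inference a reader might draw: that breast data are collected and then ignored, or that the plan keeps them out of any report. Neither is supported. What remains is narrower. None of these routes gives the number of men affected, tenderness has no analysis of its own, and permission to report more is not a commitment with a case definition.

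Two further inferences should be resisted. Section 6.1.3 lists gynecomastia alone, so the documents do not say that low-grade events, or tenderness, are common. And the fatigue figures are an analogy: the 27.1% pools doses of 30 to 600 mg/day in advanced disease and predicts nothing about breast events here.

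It is also fair that this is an exploratory single-arm phase II trial and that the data could be tabulated later. That limits the severity. It does not remove the advantage of fixing the definition beforehand.

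**Conclusion.** The point holds as a minor gap in the reporting plan. Both adverse event summaries in Section 13.2.2 are limited to grade 3 or higher treatment-related events, and Section 13 has no analysis of the yes/no breast question or of breast irradiation. Followed as written, the plan produces no incidence of breast events below grade 3 for an effect the protocol lists as common.

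The size is unknown. The tabulated rates show only that the planned table cannot distinguish 7 affected men from 35 if none reaches grade 3. How many would stay below grade 3 is itself an assumption. The conclusion about the plan depends on none of these figures, only on what Section 13 commits to. The primary endpoint, error rates, power and sample size are unaffected.

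**What to change.** In Section 13.2.2 add:

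1. Regardless of adverse event grade, the number and proportion of treated men answering yes to the breast question at any on-treatment visit (end of cycle 6 included), with an exact 90% CI.
2. New onset reported separately, with men who answered no at baseline as the denominator. Keeping baseline-yes men in that denominator would dilute the rate, since they cannot become new cases.
3. The number of men given breast irradiation under Section 6.2.1.3.

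In Section 13.2.4, state that breast diameter is included at its three visits, together with the protocol's size grade, labelled as not a CTCAE grade.

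In the calendar, state explicitly that the question is asked at baseline. The footnote says every study visit, but the asterisks mark only Cycles 2, 3, 5 and 6.

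The cost is one extra table, a few sentences of SAP text, and confirmation that the baseline answer and breast irradiation are captured on the forms. No extra patients are needed. The tolerability profile may look less favourable.
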